3.0 Outcome Measures/Endpoints

3.1 Primary Outcome Measures:

Aim 1: OT will alter alcohol tolerance. Compared to their performance under PL and respective baseline assessment, participants given intranasal OT will show, in one or more of the following, greater alcohol-related perturbation of the subjective response to alcohol, the Stroop test, and Stop Signal task performance.

3.2 Primary Outcome Measures:

Aim 2: OT will reduce motivation for alcohol. Participants will display lower motivation for alcohol under OT compared to PL, reflected by one of more of the following: During alcohol self-administration, less cumulative work for alcohol on the progressive ratio task, and reduced overall alcohol exposure as reflected by the breath alcohol concentration (BrAC) curve during alcohol self-administration; During the BrAC clamp, altered APT derived behavioral economic indices and/or reduced subjective craving for alcohol.

4.0 Eligibility Criteria

4.1 Inclusion Criteria

- Overtly healthy men and women aged 21 60.
- Heavy alcohol drinkers [greater than 14 (men) or 7 (women) drinks per week, and at least 5 binges per month, with a binge defined as 5 (men) or 4 (women) drinks on the same occasion³⁰], unless determined by PI that drinking history meets study objectives.
- Able to understand/complete questionnaires and procedures in English.
- Have venous access sufficient to allow blood sampling.

4.2 Exclusion Criteria

- Latex allergy (due to oxytocin/latex cross-reactivity).
- Nasal condition that compromises delivery and/or absorption of intra-nasal oxytocin
- Pregnant or breast-feeding women.
- Desire to be treated for any substance use disorder or court ordered to not drink alcohol
- Medical disorders or other conditions such as alcohol withdrawal seizures or delirium tremens that may influence study outcome or participant safety.
- Positive urine drug screen for amphetamines/ methamphetamines, barbiturates, benzodiazapines, cocaine, opiates, or phencyclidine if determined by the PI to adversely affect participant safety or data integrity.
- Medications (past 30 days) that could influence participant safety or data integrity (e.g. antidepressants, antipsychotics, benzodiazepines, etc.) as determined by the PI.
- DSM 5 Disorders (non-AUD) or current/history of neurological disease of cerebral origin, or head injury with > 20 min loss of consciousness, if determined by the PI to affect participant safety or data integrity.
- Positive BrAC reading at beginning of the experimental session.
- Actively suicidal (for example, any current suicidal intent, including a plan) or are at serious suicidal risk, by clinical judgment of the PI.
- Any condition for which the PI and investigative team determine it is unsafe or not prudent to enroll a participant.

5.0 Study Design

Overview: This project employs a double-blind, within-subject design. Each participant will be randomly assigned to either the clamp or self-administration condition, and be studied twice, once with intranasal administration of OT and once with intranasal PL. At least 3 weeks will elapse between each participant's tests to ensure that residual effects of OT administration have dissipated.

6.0 Enrollment/Randomization

Participants will be randomized to study session order (OT-PL or PL-OT) at time of scheduling, using a procedure that ensures an equal number of participants in each group. Stratification of other potentially key risk or analytical variables, such as sex and age distribution, will be periodically monitored and individual subject order assignment may be adjusted to achieve balance. Neither subjects nor technicians will know which session is PL, and which is OT.

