Participants: We plan to recruit up to 30 subjects in order to complete study of 10-15 heavy drinking participants (minimum 5 each in the clamp and self-administration arms). Approximately equal numbers of men and women will be recruited.

Payment: Participation fees are paid in cash at the end of each study visit, by email using an Amazon gift card, or by mail using a visa card or check. For the interview, participants will receive \$15 if they complete the online portion only, and \$25 if they complete both the online and in person portions, or complete the full interview in person. Subjects who completed and were paid for the interview for another study, and who provide only minimal updates to their information, will not be paid an additional interview fee. For the IV alcohol infusion sessions, the experimental day lasts about 11 hours; session 1 pays \$130, and session 2 pays \$200. In addition, subjects will be reimbursed for parking, bus pass or up to \$10 for taxi/ride sharing. Thus a subject can receive up to \$365 for participation. Payments are calculated to reimburse subjects at a rate of about \$15/hour if they complete all sessions; session 2 pays more than session 1 because of the increased value of the subject's participation. If an infusion session is terminated early, participants will be paid \$15 per hour, calculated in 20 min increments, for time they are at the Clinical Research Center, up to the total promised for the study day.

Method: We will assess the effects of OT on alcohol tolerance in heavy drinking participants using the computer-assisted alcohol infusion system (CAIS; Figure 1) developed³⁰⁻³² and maintained at Indiana University with the support of the Indiana Alcohol Research Center. Individual characteristics (height, weight, age and sex) are used to compute physiologically-based pharmacokinetic models of the distribution and elimination of alcohol⁴¹⁻⁴², which in combination with model-based control techniques, allows for the precise control of breath, and therefore arterial and brain, alcohol concentrations⁴³. CAIS IV alcohol techniques span a

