the first developed and most common IV alcohol paradigm. Breath alcohol concentration (BrAC) is raised to a target level, usually within 15-20 minutes, that can then be maintained ("clamped") at or near the target for whatever duration is necessary for a specific study. Recently, CAIS-based alcohol self-administration paradigms have been developed that provide the participants with control over individual alcohol increments that are virtually identical within and across participants. The overall alcohol exposure differs due to the participant's choice of timing and number of increments (see Figure 3, Alcohol Self-Administration phase). CAIS IV techniques allow investigators to study the higher BrAC typical of heavy drinkers safely, both due to the reduced variability of each incremental exposure and because BrAC immediately descends upon termination of the infusion; after oral intake, the BrAC continues to rise until absorption is complete. In addition, IV alcohol infusion reduces expectancy effects (arising from sight, odor, taste and the physical act of drinking), without affecting the subjective effects associated with intoxication⁴⁶. In the present study, half of the subjects will be tested using a BrAC clamp to assess performance on a battery of perceptive, cognitive and behavioral tests, and half of the subjects will be tested in a self- administration session for a direct measure of motivation for alcohol and self-selected BrAC, consistent with our prior work.

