Study day procedures: Upon arrival at the Indiana Clinical Research Center (ICRC), participants will be rescreened for drug use, pregnancy (if applicable), and BrAC. Participants are asked to abstain from alcohol after 8:00 pm the night before each session and must have a BrAC of zero at the beginning of an infusion. We will record the participant's recent drinking using a TLFB. Car keys will be held for safekeeping. Using sterile technique, an indwelling catheter will be placed in a vein of one arm. For the clamp, only a single pump is needed to deliver alcohol. For self-administration, the catheter will be connected to the two infusion pumps, one of which is used to deliver saline as the alternative reward; the second delivers ethanol infusate prepared by IU Health Investigational Drug Services (IDS) by mixing sterile half-normal saline with 95% sterile ethanol to create an approximately 6.0% (v/V) solution. Infusate concentration is checked using a refractometer prior to the start of the session and the result incorporated into the infusion profile determination. After the catheter is placed, a standardized 550 calorie breakfast is served. Testing will be performed in one of the lab's 5'x7' Industrial Acoustic Corporation[®] sound-dampened chambers or in a private room in the ICRC. Testing location will be identical across sessions for each subject. When testing is done in the lab chambers, a closed-loop intercom system enables the participant to talk to the technician at any time without manual effort. When testing is done in a private room in the CRC, technicians will be located behind a curtain and immediately available to the subject whenever needed.

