Session procedures: Self-administration (Figure 4). During the 150 min alcohol self-administration session, the participant initiates each work-set by choosing between 1 of 2 rewards, either alcohol or water. Work-sets consist of trials of the Constant Attention Task, or CAT (Figure 5), developed by our laboratory and with demonstrated sensitivity to pharmacogenomics and sex effects^{38, 39}. Successive rewards require an increasing number of successful CAT trials. The work schedules required to obtain water or alcohol are identical, but progress is tracked separately and not communicated to the participants. Throughout any workset, participants are free to wait, work ad-lib, pause, or cease working. The available rewards are a standardized increment in BrAC (alcohol, labeled "A") or an infusion of saline (water, labeled "W"), each delivered over 2.5 min. Reward delivery begins immediately after the last correct CAT trial required for the work-set is performed. Alcohol reward increments raise the participant's BrAC by 10.0 mg/dL in 2.5 min before declining at a steady rate of -0.8 mg/dl/min, until the next alcohol reward is delivered or as long as pharmacokinetically possible. CAIS continuously estimates the future time course of BrAC and prohibits infusion that would vield a BrAC exceeding the predetermined, ecologically valid safety limit (180 mg/dL in this heavy alcohol drinking sample). The first dose of OT or PL will be administered 30 min before the start of the self-administration phase, and consist of 10 intranasal puffs [insufflations] alternating every 30 seconds between nostrils, delivering in total 40 IU of OT in 1 ml of solution or 1 ml of PL solution. Booster doses of 24 IU of OT will be given approximately hourly after the initial dose. Participants will complete the subjective perceptions assessment and side effects questionnaire prior to the first OT/PL administration, immediately before the start of alcohol self-administration, and at 20 min intervals throughout the session, timed with alcohol reward increments when possible. Except for ad-libitum bathroom breaks, participants remain in the chamber or room for the duration of the experiment; technician interaction is limited to occasional BrAC samples, data collection, and verbal checks to assure subject comfort at the beginning/end of each intervention.

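### Section 6.0 lets an individual's session order be adjusted after randomisation and does not tie the promised equal orders to the two arms in which OT is mostly compared with PL

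*Combined protocol and SAP*

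**What the plan says.** Section 6.0 randomises session order at scheduling, "using a procedure that ensures an equal number of participants in each group". In context the groups are the two orders, OT then PL and PL then OT. Other variables are then monitored periodically. Sex and age are given as examples, and "individual subject order assignment may be adjusted to achieve balance". On blinding, the section says: "Neither subjects nor technicians will know which session is PL, and which is OT".

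Arm is a separate assignment. Section 5.0 says: "Each participant will be randomly assigned to either the clamp or self-administration condition". Section 7.0 plans 10 to 15 completers in all, "minimum 5 each in the clamp and self-administration arms", and says that "half of the subjects will be tested using a BrAC clamp". No section links the order randomisation to the arm.

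Section 12.0 compares OT with PL within person by paired t-tests, accommodating baselines where appropriate. It mentions no period or sequence term, and it excludes anyone who completes only one session.

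**The concern.** There are two gaps.

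First, the adjustment clause has no rule, trigger, timing or responsible role. It could mean steering assignments not yet made or changing ones already made. Either way, the text does not show that adjusted assignments are random or concealed.

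Second, equal orders overall do not guarantee equal orders within an arm. Stroop, Stop Signal and the Alcohol Purchase Task under alcohol exist only in the clamp arm; work for alcohol and BrAC exposure exist only in the self-administration arm. Subjective perceptions and craving are collected in both, but pooling is not described. When orders are unequal in an arm, part of any change from session 1 to session 2 is counted as an OT effect.

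The clamp battery has a pre-drug baseline that can absorb a session-wide shift. Self-administered work and exposure have none: "The first dose of OT or PL will be administered 30 min before the start of the self-administration phase". What is at stake is mainly the estimate, because the study's stated purpose is to supply data in support of a larger, properly powered trial.

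**Working it through.** The plan gives no figure for order balance, period effect, alpha or power, so there is nothing to reproduce. The adjustment clause cannot be quantified from the documents. The steps below concern balance within arm.

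**Inputs from the plan.** Two orders in equal numbers (6.0); separate arm assignment (5.0); half the participants per arm, at least 5 completers each, 10 to 15 in all (7.0); paired t-test (12.0). I take 5+5 and 7+7 completers.

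**Assumptions.** Orders exactly equal among all completers; period effect p of 0.25 to 0.5 SD of the within-person difference; two-sided 5% test. None of these is stated in the plan for completers.

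**1. Chance of an uneven arm.** The number of OT-first people in an arm of n is hypergeometric: P(a) = C(n,a)² / C(2n,n).

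- 5+5: 3:2 has probability 200/252 = 79.4%; 4:1 or worse has 52/252 = 20.6%.
- 7+7: 4:3 has 2450/3432 = 71.4%; 5:2 or worse has 982/3432 = 28.6%.
- If dropout destroys overall equality, independent 50:50 orders give upper references of 12/32 = 37.5% and 58/128 = 45.3%.

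**2. Share of the period effect entering the estimate.** If session 2 differs from session 1 by p, OT minus PL shifts by −p for OT-first people and +p for PL-first people. The mean shifts by p × f in absolute size, where f = |n₁ − n₂| / n.

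| Split | f | Bias at p = 0.25 to 0.5 SD | Standard error 1/√n |
|---|---|---|---|
| 3:2 | 0.20 | 0.05 to 0.10 SD | 0.45 SD |
| 4:1 | 0.60 | 0.15 to 0.30 SD | 0.45 SD |
| 4:3 | 0.14 | 0.04 to 0.07 SD | 0.38 SD |
| 5:2 | 0.43 | 0.11 to 0.21 SD | 0.38 SD |

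**3. Error averaged over the splits.** If order is random, each imbalance is equally likely in either direction, so the expected signed bias is zero. What remains is added variance: RMSE = √(1/n + p² E[f²]).

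- 5+5: E[f²] = (200×0.04 + 50×0.36 + 2×1)/252 = 28/252 = 1/9. With balance within arm, f² = 0.04.
- 7+7: E[f²] = (2450×1/49 + 882×9/49 + 98×25/49 + 2×1)/3432 = 264/3432 = 1/13. With balance within arm, f² = 1/49.

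| n per arm | p | Overall balance only | Balanced within arm | Reduction |
|---|---|---|---|---|
| 5 | 0.25 | 0.455 | 0.450 | 1.1% |
| 5 | 0.5 | 0.477 | 0.458 | 4.0% |
| 7 | 0.25 | 0.384 | 0.380 | 1.2% |
| 7 | 0.5 | 0.403 | 0.385 | 4.5% |

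**4. False-positive rate of the paired t-test (simulation, no OT effect).** At p = 0.25 and 0.5 SD it is about 4.5% and 3.5% at 3:2, 5.4% and 6.4% at 4:1, 4.5% and 3.3% at 4:3, and 5.1% and 5.4% at 5:2. Averaged over the splits in step 1, it lies between about 4.0% and 4.8% in all four cases, below the nominal 5%.

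**The case against.** The case against is substantial. This is a self-described exploratory pilot. Steering assignments on covariates is a recognised approach, so the clause may lack only reporting detail. The list of monitored variables is open and could include arm. The protocol controls some sources of a period effect: same test location, a task that adapts to practice and fatigue, and a precaution about discharge time. On average nothing is biased and the test is not inflated. Removing hand balancing also gives up control of sex, although sections 7.0 and 12.0 report sex effects with these methods.

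Most of this stands and limits the point to a modest one. It does not remove it. Arm is not named among the monitored variables, and an open list with no rule assures nothing. The discharge-time precaution shows that the protocol itself recognises that second-session behaviour may differ from the first. A sex difference in level cancels within person, so sex balance across orders matters less than order balance within arm.

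A reader might go further and infer that whoever adjusts the order must know it, that the blind is therefore broken, and that the investigator's discretion to end participation is exercised with that knowledge. The documents do not support this. Balance can be monitored and steered between two coded sequences without knowing which is OT first. No text says that the investigator makes the adjustment, and section 5.0 describes the trial as double-blind.

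**Conclusion.** The point holds as a modest design improvement. The text of section 6.0 permits adjustment of individual orders without a rule and does not secure equal orders in the arms where most contrasts are made. An arm of 5 is 4:1 or worse with probability 20.6%, and an arm of 7 is 5:2 or worse with 28.6%, assuming exact overall equality among completers. In such an arm, 60% (at 4:1) or 43% (at 5:2) of any period effect enters the OT estimate.

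The expected loss is small: about 1 to 5% of root-mean-square error before dropout, for period effects of 0.25 to 0.5 SD that are assumed and not documented. Even in the uneven arms tabulated, the bias stays below the standard error. It would be wrong to conclude that the plan inflates false positives overall, or that the blind has been compromised. The case for change rests on how little it costs.

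**What to change.** In section 6.0, delete the words "individual subject order assignment may be adjusted to achieve balance" and state:

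*After arm is assigned, session order is the next entry on that arm's list, generated before enrolment in permuted blocks of 2 and 4 in random sequence and held by a role outside enrolment, testing and analysis. No order is changed after assignment.*

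In section 12.0, keep the paired t-test and add:

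*Order counts among completers are reported per arm; if all completers in an arm have one order, the report states that OT and period cannot be separated there.*

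The cost is one list per arm and two wording changes. Sex and age are no longer balanced by hand across orders, a small loss because each participant is their own control.

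The lists hold an arm of 5 at 3:2 and an arm of 7 at 4:3 only before dropout. In simulation, with dropout independent of order and enrolment continuing until 5 complete, 4:1 or worse still occurs in about 8%, 14% and 22% of arms at assumed dropout of 20%, 33% and 50%. The plan gives no dropout rate, which is why the counts among completers should be reported.

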7.0 Study Procedures

Recruitment and Screening

We expect to recruit most of the participants for this study from our database of subjects who have completed a past experiment and have consented to be contacted for additional studies. Some participants may learn about the study from print, electronic advertising, or word of mouth, and then contact our phone line or visit the study website. Participants who meet basic criteria will be invited for an interview. Participants who have not previously completed an interview in our lab will complete a full interview. Participants who have interview data on record may be asked to update some interview information as needed for participant safety or data integrity. Updates may be done by phone, online, or in person. Interview measures may include some or all of the following measures, at the discretion of the principal investigator:

Self-Report Measures:

- The Alcohol Use Disorders Identification Test (AUDIT)
- The Urgent Premeditation, Perseverance, Sensation Seeking and Positive Urgency (UPPS-P) Impulsive Behaviors Scale measures impulsivity traits, including urgency.
- Self-Rating of Effect of Alcohol assessing retrospective sensitivity to the subjective response to alcohol (SRE).
- Short Inventory of Problems Revised (SIP-r)
- Medical History (including menstrual phase for women)
- Nicotine History Measure
- Penn Alcohol Craving Scale (PACS)

Interviews:

- Brief medical history (including menstrual phase for women)
- The Semi-Structured Assessment for the Genetics of Alcoholism IV (SSAGA-IV), Alcohol
- The Semi-Structured Assessment for the Genetics of Alcoholism IV (SSAGA-IV), Family History of Alcoholism

Diary Measures:

• Timeline Follow-back (TLFB) modified to assess for one-month recall of alcohol use

Screening tools:

- Clinical Institute Withdrawal Assessment for Alcohol Scale (CIWA)
- Generalized Anxiety Disorder Assessment (GAD-2, GAD-7). Anxiety symptoms over the last 2 weeks are queried in a 2 item scale which expands to 5 additional items if the first 2 are endorsed.
- Patient Health Questionnaire (PHQ-2 and PHQ-9). Depressive symptoms over the last 2 weeks are queried in a 2 item scale which expands to 7 additional items if the first 2 are endorsed.
- Urine pregnancy and drug screen (UPS, UDS, the latter including EtG urine screen at discretion of PI)
- Breath Alcohol Concentration (BrAC) Measurement
- Liver function assessment (standard liver panel)

Participants: We plan to recruit up to 30 subjects in order to complete study of 10-15 heavy drinking participants (minimum 5 each in the clamp and self-administration arms). Approximately equal numbers of men and women will be recruited.

Payment: Participation fees are paid in cash at the end of each study visit, by email using an Amazon gift card, or by mail using a visa card or check. For the interview, participants will receive \$15 if they complete the online portion only, and \$25 if they complete both the online and in person portions, or complete the full interview in person. Subjects who completed and were paid for the interview for another study, and who provide only minimal updates to their information, will not be paid an additional interview fee. For the IV alcohol infusion sessions, the experimental day lasts about 11 hours; session 1 pays \$130, and session 2 pays \$200. In addition, subjects will be reimbursed for parking, bus pass or up to \$10 for taxi/ride sharing. Thus a subject can receive up to \$365 for participation. Payments are calculated to reimburse subjects at a rate of about \$15/hour if they complete all sessions; session 2 pays more than session 1 because of the increased value of the subject's participation. If an infusion session is terminated early, participants will be paid \$15 per hour, calculated in 20 min increments, for time they are at the Clinical Research Center, up to the total promised for the study day.

Method: We will assess the effects of OT on alcohol tolerance in heavy drinking participants using the computer-assisted alcohol infusion system (CAIS; Figure 1) developed³⁰⁻³² and maintained at Indiana University with the support of the Indiana Alcohol Research Center. Individual characteristics (height, weight, age and sex) are used to compute physiologically-based pharmacokinetic models of the distribution and elimination of alcohol⁴¹⁻⁴², which in combination with model-based control techniques, allows for the precise control of breath, and therefore arterial and brain, alcohol concentrations⁴³. CAIS IV alcohol techniques span a

Figure 1. Schematic of CAIS system, including computer specifications, software, and accessories. The CAIS system consists of PC-based software interfacing with iv infusion pumps. Prior to infusion, the participant's age, height, weight, and gender are entered into the software, which transforms those measurements into parameters of a physiologically-based pharmacokinetic (PBPK) model of alcohol distribution and elimination. Infusate and breath alcohol concentration measurements provide feedback to adjust the PBPK model for each participant. Computation of the infusion rate profile is based on the updated model to achieve virtually identical clamp then incremental exposures to alcohol across participants. The subject and the infusion rate profile are monitored at all times by a technician.

broad range of applications, from the assessment of initial sensitivity and tolerance using the alcohol clamp³¹⁻³⁷ to the assessment of alcohol self-administration ³⁹⁻⁴⁰. The need for controlled IV alcohol administration is illustrated in Figure 2 - Top, which shows the wide variation in alcohol exposure within and across individuals resulting from oral challenge paradigms. In contrast, (Figure 2 – Bottom) shows data from an alcohol clamp,

Figure 2.

Top. Individual BrAC trajectories in ingestion. Alcohol ingestion yields variable trajectories of BrAC. Exposure trajectories after ingestion of a dosage normalized by total body water to produce a peak BrAC of 80 mg/dL under standardized conditions for 44 participants is displayed^{44,45}.

Bottom. BrAC clamping trajectories. BrAC clamping experiment conducted in 50 young adults with the goal of raising BrAC to 60 mg/dl in 10 minutes, then maintaining it for 3 hours. The result minimizes the variability in BrAC trajectories across participants^{44.45}.

the first developed and most common IV alcohol paradigm. Breath alcohol concentration (BrAC) is raised to a target level, usually within 15-20 minutes, that can then be maintained ("clamped") at or near the target for whatever duration is necessary for a specific study. Recently, CAIS-based alcohol self-administration paradigms have been developed that provide the participants with control over individual alcohol increments that are virtually identical within and across participants. The overall alcohol exposure differs due to the participant's choice of timing and number of increments (see Figure 3, Alcohol Self-Administration phase). CAIS IV techniques allow investigators to study the higher BrAC typical of heavy drinkers safely, both due to the reduced variability of each incremental exposure and because BrAC immediately descends upon termination of the infusion; after oral intake, the BrAC continues to rise until absorption is complete. In addition, IV alcohol infusion reduces expectancy effects (arising from sight, odor, taste and the physical act of drinking), without affecting the subjective effects associated with intoxication⁴⁶. In the present study, half of the subjects will be tested using a BrAC clamp to assess performance on a battery of perceptive, cognitive and behavioral tests, and half of the subjects will be tested in a self- administration session for a direct measure of motivation for alcohol and self-selected BrAC, consistent with our prior work.

Study day procedures: Upon arrival at the Indiana Clinical Research Center (ICRC), participants will be rescreened for drug use, pregnancy (if applicable), and BrAC. Participants are asked to abstain from alcohol after 8:00 pm the night before each session and must have a BrAC of zero at the beginning of an infusion. We will record the participant's recent drinking using a TLFB. Car keys will be held for safekeeping. Using sterile technique, an indwelling catheter will be placed in a vein of one arm. For the clamp, only a single pump is needed to deliver alcohol. For self-administration, the catheter will be connected to the two infusion pumps, one of which is used to deliver saline as the alternative reward; the second delivers ethanol infusate prepared by IU Health Investigational Drug Services (IDS) by mixing sterile half-normal saline with 95% sterile ethanol to create an approximately 6.0% (v/V) solution. Infusate concentration is checked using a refractometer prior to the start of the session and the result incorporated into the infusion profile determination. After the catheter is placed, a standardized 550 calorie breakfast is served. Testing will be performed in one of the lab's 5'x7' Industrial Acoustic Corporation[®] sound-dampened chambers or in a private room in the ICRC. Testing location will be identical across sessions for each subject. When testing is done in the lab chambers, a closed-loop intercom system enables the participant to talk to the technician at any time without manual effort. When testing is done in a private room in the CRC, technicians will be located behind a curtain and immediately available to the subject whenever needed.

Figure 3: Alcohol Clamp. Diagram of the experimental session showing test batteries (orange boxes), OT and PL administrations (green boxes), alcohol clamp (grey box) and example subject breath alcohol concentrations (colored lines). **Experimental timeline:** Min 0-30: Baseline battery. Min 30-35: Intranasal OT or PL administered. Min 35-60: Pause for drug absorption. Min 60-90: OT/PL battery. Min 90-105: OT/PL booster dose at the beginning of a 15 min alcohol infusion ramp (4 mg/dL/min) to bring BrAC to 60 mg/dL. Min 110-140: Alcohol+OT or Alcohol+PL battery assessing initial response to alcohol during BrAC clamp at 60 mg/dL. Min 180-182.5: Booster dose of OT or PL. Min 200-230: Alcohol+OT or Alcohol+PL battery assessing adapted response to alcohol during BrAC clamp at 60 mg/dL.

Session procedures: Alcohol Clamp (Figure 3). Clamp sessions begin with a baseline battery lasting approximately 30 min and consisting of the Stop Signal Task (a motor impulsivity task that has demonstrated sensitivity to alcohol exposure); a subjective perceptions assessment, including craving; a side effects questionnaire; the Alcohol Purchase Task (a cognitive test providing measures of behavioral economics, revised for use during iv infusion); and the Stroop Test of mental concentration (accuracy and speed stating the color of a series of words printed in colors different from the colors they actually name). The battery is repeated after an initial dose of OT or PL, and at the beginning and end of a 2 h clamp, with booster doses of OT or PL 20 min prior to each of the clamp batteries. The dosing schedule of oxytocin relative to testing is derived from studies suggesting onset of effects in approximately 30 minutes and a duration of approximately 60 minutes⁴⁸⁻⁵¹. The first dose of OT or PL will consist of 10 intranasal puffs [insufflations] alternating every 30 seconds between nostrils, delivering in total 40 IU of OT in 1 ml of solution or 1 ml of PL solution. A 20-30 min drug absorption period follows the first dose; booster doses of 24 IU of OT will be given 20 min prior to each of the remaining 2 test batteries. During the intervals between test batteries, the participant will be free to rest, read, or use an electronic device for entertainment.

Figure 4: Alcohol Self-Administration session: Diagram of the experimental test session showing timing of OT/PL administration relative to the alcohol self-administration phase. The array of lines during the alcohol self-administration phase, derived from subject data from a past experiment, reflects a range of possible behavior, limited by the 180 mg/dL safety limit and the increasing demands of the progressive work schedule.

Session procedures: Self-administration (Figure 4). During the 150 min alcohol self-administration session, the participant initiates each work-set by choosing between 1 of 2 rewards, either alcohol or water. Work-sets consist of trials of the Constant Attention Task, or CAT (Figure 5), developed by our laboratory and with demonstrated sensitivity to pharmacogenomics and sex effects^{38, 39}. Successive rewards require an increasing number of successful CAT trials. The work schedules required to obtain water or alcohol are identical, but progress is tracked separately and not communicated to the participants. Throughout any workset, participants are free to wait, work ad-lib, pause, or cease working. The available rewards are a standardized increment in BrAC (alcohol, labeled "A") or an infusion of saline (water, labeled "W"), each delivered over 2.5 min. Reward delivery begins immediately after the last correct CAT trial required for the work-set is performed. Alcohol reward increments raise the participant's BrAC by 10.0 mg/dL in 2.5 min before declining at a steady rate of -0.8 mg/dl/min, until the next alcohol reward is delivered or as long as pharmacokinetically possible. CAIS continuously estimates the future time course of BrAC and prohibits infusion that would vield a BrAC exceeding the predetermined, ecologically valid safety limit (180 mg/dL in this heavy alcohol drinking sample). The first dose of OT or PL will be administered 30 min before the start of the self-administration phase, and consist of 10 intranasal puffs [insufflations] alternating every 30 seconds between nostrils, delivering in total 40 IU of OT in 1 ml of solution or 1 ml of PL solution. Booster doses of 24 IU of OT will be given approximately hourly after the initial dose. Participants will complete the subjective perceptions assessment and side effects questionnaire prior to the first OT/PL administration, immediately before the start of alcohol self-administration, and at 20 min intervals throughout the session, timed with alcohol reward increments when possible. Except for ad-libitum bathroom breaks, participants remain in the chamber or room for the duration of the experiment; technician interaction is limited to occasional BrAC samples, data collection, and verbal checks to assure subject comfort at the beginning/end of each intervention.

Figure 5: The CAT task. Subjects initiate the task by pressing down on one of two buttons, labeled "A" (alcohol) or "W" (Water). Holding the button down results in a screen graphic showing the choice button ("A" in this example) surrounded by a yellow circle. When the yellow changes to blue, the subject must release as quickly as possible. On release, the circle returns to white and the subject must indicate whether they thought they were successful. The screen graphic then shows green for successful release, and red for an unsuccessful (too slow) release. The task adapts by increasing the release time window required after errors, and decreasing it after successes. Thus, the percent of successful trials remains constant across subjects and is not affected by basal reaction time, practice, fatigue, or intoxication.

Recovery/Discharge procedures: Alcohol clamp sessions. Upon completion of the alcohol clamp, participants will stay in an inpatient room until they can be safely discharged with a BrAC <35mg/dL. They are served lunch from the ICRC kitchen. Subjects will be told that they should expect to stay at the CRC until 7:00 pm, although they will be dismissed earlier if their BrAC is below 35 mg/dL. Participants with a BrAC > 35 mg/dL at 7:00 pm will be compensated at the rate of \$15/hour in 20-minute increments for the time stayed past 7:00 pm. Participants staying past 5:00 pm will be offered dinner.

Recovery/Discharge procedures, Alcohol self-administration sessions. Subjects participating in the selfadministration sessions will be required to stay until at least 7:00 pm and until BrAC < 35 mg/dL, whichever is later. Participants are served lunch from the ICRC kitchen; they will also be given dinner at about 5:30 pm. Participants with a BrAC of 35 mg/dl or below but who show signs of intoxication and/or self-report any concerns regarding their safe passage home at the time of discharge will be provided transport home via car service. Participants with a BrAC > 35 mg/dL at 7:00 pm will be compensated at the rate of \$15/hour in 20minute increments for the time stayed past 7:00 pm in a payment made at the second session. Any participants who must stay past 7:00 pm for the first session will be informed that they have to stay until the same time for the second session (in order to reduce discharge-motivated drinking behavior during the second session compared to the first). However, for the second session, participants will only actually be required to stay past 7:00 pm if their BrAC remains at or above 35 mg/dL or if a concern regarding their ability to be safely discharged exists. At the discretion of the PI, subjects may be discharged before 7:00 pm if their BrAC is at or below 35 mg/dL and an early discharge would not jeopardize subject safety or study objectives.

